5.5.2 Categories

The following two categories are to be considered for previous and concomitant therapies:

- Drugs/therapies including, but not limited to, prescription, over-the-counter (OTC), birth control pills/patches/hormonal devices, vitamins, moisturizers, sunscreens, herbal medicines/supplements, and homeopathic preparations.
- Medical and surgical procedures including, but not limited to, laser/radiation procedures, dermal fillers, X-rays (excluding dental X-rays), etc.

5.5.3 Recording

Previous and concomitant therapies are to be recorded on the Drugs/Therapies form (for drugs/therapies) and/or on the Medical and Surgical Procedures form (for medical/surgical procedures) in the case report form (CRF).

Concomitant therapies (including preferred or provided moisturizer) are to be recorded, reviewed, and updated at each visit. Every attempt should be made to keep concomitant therapy dosing and regimen constant during the trial.

5.5.4 Authorized concomitant therapies

Unless listed under the exclusion criteria (Section 5.4 item [15]) or in prohibited concomitant therapies, the following therapies are allowed, as long as they are not indicated for the treatment of acne vulgaris (see Section 5.5.5):

Topical treatments:

In addition to the study drug, the following **CCI** products are authorized on the treated areas if they are not indicated for the treatment of Acne Vulgaris:

CCI

5.5.5 Prohibited concomitant therapies

CCI

CCI

If prohibited therapies become a necessary treatment for the safety or best interest of the subject, GALDERMA should be notified to discuss possible alternatives prior to administration of a prohibited therapy.

If a subject receives prohibited therapy during the clinical trial, GALDERMA should be notified to discuss the pertinence and the modalities for the subject to continue in the clinical trial.

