11.6	Insurance	69
12	LITERATURE REFERENCE LIST.....	69
13	APPENDICES	72
13.1	Subject Satisfaction Questionnaire.....	72
13.2	Study Drug Acceptability Questionnaire	74
13.3	Dermatology Life Quality Index (DLQI™).....	75
13.4	Children’s Dermatology Life Quality Index (C-DLQI™)	77
13.5	QOL Questionnaire for Face and Trunk Acne (16 years of age and older)	79
13.6	EuroQoL 5-Dimension (EQ-5D-5L)	81
13.7	Fitzpatrick Skin Classification.....	83
13.8	Acne Harmonization Lesion Count	84
CCI		
13.10	Atrophic Acne Scar Counts.....	87
	Protocol Signature Page.....	88

List of Tables

Table 1	Clinical trial schematic	13
Table 2	Schedule of assessments	14
Table 3	Exit Form reasons for discontinuation	31
Table 4	Description and usage of the study drug	32
Table 5	Suspected sensitization - reaction grading	49
Table 6	Suspected sensitization - conclusion	49

SYNOPSIS	
Clinical Trial Title: A Multi-Center Study to Evaluate Subject Reported Outcomes with use of Trifarotene 50 µg/g Cream in the Treatment of Moderate Facial and Truncal Acne Vulgaris	
Short Title: Subject Reported Outcomes with use of Trifarotene 50 µg/g Cream in Subjects with Moderate Facial and Truncal Acne Vulgaris	
Lay Title: Studying the Effects of 50µg/g Cream on Subjects who have Acne	
Clinical Trial phase:	IIIb
Clinical Trial Population:	Subjects with moderate acne vulgaris with facial and truncal acne involvement
Clinical Trial objectives:	The purpose of this study is to evaluate subject reported outcomes with Trifarotene cream.
Clinical Trial design:	Multi-center, open label, single arm study of Trifarotene cream applied once daily in the evening for 24 weeks.
Total number of subjects (Planned):	Approximately 50 subjects will be enrolled in order to obtain 40 subjects at completion.
Number of clinical trial centers (Planned):	CCI [REDACTED]
Region(s) / country(ies) involved (Planned):	United States
Clinical trial duration:	CCI [REDACTED]
Duration of subject participation:	Clinical trial participation for each subject is approximately 24 weeks of study treatment ±3 days. Note: Subjects, upon study completion/early termination, will return to standard of care with their physician.
Key inclusion criteria	
 1. Male or female, 9 years of age and older, at the Screening visit. 2. The Subject has a facial acne CCI [REDACTED]. CCI [REDACTED]

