9.2 Sample size determination

There is no formal hypothesis to be tested. An estimation approach will be performed. Point estimate and 95% confidence interval will be constructed. Approximately 50 subjects will be enrolled to evaluate the subject reported outcomes (quality of life and satisfaction survey).

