6.3. Imputation of Missing Data

The last observation carried forward (LOCF) will be used to impute efficacy endpoints, where applicable. If no post-baseline observations are available, baseline observation will be carried forward.

Non-responder analysis will also be carried out for binary endpoints by imputing missing data using the missing as failure (MAF) method.

No imputations will be performed for safety analyses.

CCI [REDACTED]

CCI [REDACTED]

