7.5. Medications

CCI

All medications will be listed.

CCI

CCI

8. Efficacy

All efficacy assessments will be summarized by visit using descriptive statistics. A two-sided 95% Clopper-Pearson confidence interval (CI) for success rate and a two-sided 95% Student's t-distribution CI for mean values will be included in the efficacy summary tables, if applicable.

Efficacy analyses will be performed with the observed cases (OC) and with last observation carried forward (LOCF) for data imputation for Investigator's Global Assessment (IGA), Physician's Global Assessment (PGA) and acne lesions counts on the face and trunk. Non-responder analysis will also be carried out for binary endpoints by with missing as failure (MAF) for data imputation.

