8.1. Efficacy Endpoints and Analysis

8.1.1. CCI [REDACTED]

The Investigator's Global Assessment (IGA) is an instrument to evaluate the facial acne severity CCI [REDACTED]. IGA will be recorded in the CRF CCI [REDACTED] using a 5-point scale, as described in Table 3.

Table 3: Scale for acne assessment

0	Clear	Clear skin with no inflammatory or non-inflammatory lesions.
1	Almost Clear	A few scattered comedones and a few small papules.
2	Mild	Easily recognizable; less than half the surface is involved. Some comedones and some papules and pustules.
3	Moderate	More than half of the surface is involved. Many comedones, papules and pustules. One nodule may be present.
4	Severe	Entire surface is involved. Covered with comedones, numerous papules and pustules. Few nodules may be present.

IGA will be summarized by visit CCI [REDACTED] as categorical variables. All IGA data will be listed.

IGA treatment success is defined as 0 (clear) or 1 (almost clear) and at least a 2-grade improvement from baseline. The IGA treatment success rate will be summarized by visit CCI [REDACTED].

Analyses will be performed with LOCF and MAF for data imputation and with the observed cases (OC).

For the LOCF analysis, the imputation will be performed based on the recorded IGA per visit, and the imputed IGA treatment success rate will be based on the imputed values. For the MAF analysis, non-evaluable subjects will be considered as IGA treatment failures. For both LOCF and MAF analyses, the IGA treatment success rate will be calculated as the ratio between the number of subjects achieving IGA treatment success CCI [REDACTED] and the number of subjects included in the ITT population.

For the OC analysis, the IGA treatment success rate will be calculated as the ratio between the number of subjects achieving IGA treatment success CCI [REDACTED] and the number of subjects evaluable at each visit (i.e. the ones with data available at that visit).

IGA treatment success rate (LOCF) will be presented using line plots over time.

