8.1.2. Physician's Global Assessment of truncal acne

The Physician's Global Assessment (PGA) is an instrument to evaluate the truncal acne severity CCI

PGA will be recorded in the CRF and assessed CCI using the 5-point scale as described in Table 3.

PGA will be summarized by visit CCI as categorical variables. All PGA data will be listed.

PGA treatment success is defined as 0 (clear) or 1 (almost clear) and at least a 2-grade improvement from baseline. The PGA treatment success rate will be summarized by visit CCI

Analyses will be performed with LOCF and MAF for data imputation and with the observed cases (OC).

For the LOCF analysis, the imputation will be performed based on the recorded PGA per visit, and the imputed PGA treatment success rate will be based on the imputed values. For the MAF analysis, non-evaluable subjects will be considered as PGA treatment failures. For both LOCF and MAF analyses, the PGA treatment success rate will be calculated as the ratio between the number of subjects achieving PGA treatment success CCI and the number of subjects included in the ITTT population.

For the OC analysis, the PGA treatment success rate will be calculated as the ratio between the number of subjects achieving PGA treatment success CCI and the number of subjects evaluable at each visit (i.e. the ones with data available at that visit).

PGA treatment success rate (LOCF) will be presented using line plots over time.

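### In the readable text, clearance reached after a prohibited acne therapy still counts as success under all three planned rules, and there is no control arm to show it

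*Protocol*

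**What the plan says.** **Therapy rules.** Protocol 5.5.4 permits other treatments on a condition: "the following therapies are allowed, as long as they are not indicated for the treatment of acne vulgaris". Protocol 5.5.5 foresees that a prohibited therapy may become necessary for a subject's safety or interest. Once one has been taken, "GALDERMA should be notified to discuss the pertinence and the modalities for the subject to continue in the clinical trial". The readable text does not require withdrawal and does not say how later scores are to be used.

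**Success rules.** SAP 8.1.1 (IGA, face) and 8.1.2 (PGA, trunk) define success by a score of 0 or 1 together with a gain of at least two grades. Concomitant therapy does not enter the definition. LOCF starts from the recorded scores. OC uses the subjects who have data at the visit. On the non-responder analysis, SAP 6.3 says: "Non-responder analysis will also be carried out for binary endpoints by imputing missing data using the missing as failure (MAF) method". The endpoint sections repeat this in their own terms: "For the MAF analysis, non-evaluable subjects will be considered as IGA treatment failures" and "For the MAF analysis, non-evaluable subjects will be considered as PGA treatment failures".

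**Setting.** The trial is open label with a single arm. Protocol 9.2 states: "There is no formal hypothesis to be tested. An estimation approach will be performed". The opening of SAP section 8 plans "A two-sided 95% Clopper-Pearson confidence interval (CI) for success rate". On size, the protocol synopsis says: "Approximately 50 subjects will be enrolled in order to obtain 40 subjects at completion".

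**The concern.** The Week 12 and Week 24 success rates will be read as describing trifarotene cream. If a subject can add another acne treatment, remain in the trial and be scored as a success, the rate describes trifarotene plus whatever was added. A controlled trial would offer a comparison arm in which added therapy could also be seen; this trial has none.

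The three planned analyses look like a range of assumptions, but they differ only in how they treat absent data. None of them varies when the score is present and was reached on other acne therapy. How much of this enters the rates depends on individual continuation decisions made in an open-label study.

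The figures also have an audience. SAP section 2 foresees their use in regulatory submissions, publications and promotional material, so the point estimates matter even though no hypothesis is tested.

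**Working it through.** **1. The plan's own figure.** No power or precision calculation is given, so there is none to reproduce. The enrolment figure can only be checked for consistency: 1 − 40/50 = 0.20, and 40/(1 − 0.20) = 50. The 20% is derived from the same two numbers, so this is not independent confirmation. It does supply the denominators: 50 for all enrolled subjects (the synopsis definition of ITT), and about 40 for OC if only completers are observed at Week 24.

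**2. The stated rules applied to one case.** Take a subject who starts a prohibited acne therapy after Week 12, continues, and has an observed Week 24 score of 0 or 1 with a 2-grade gain.

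| Rule | What it looks at | Result at Week 24 |
|---|---|---|
| OC | whether data exist at the visit | success |
| LOCF | the recorded score | success |
| MAF | whether the subject is missing or non-evaluable | success |

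The MAF row depends on what non-evaluable means. SAP 8.1.1 and 8.1.2 explain evaluable, for OC, as having data available at that visit, and SAP 6.3 describes MAF as imputation of missing data. An observed score is evaluable in that sense. A therapy started after Week 12 cannot affect the Week 12 rate; one started earlier can affect both.

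**3. Whether anything else removes the case.** The synopsis defines ITT as all enrolled subjects. The SAP glossary lists ITT, ITTT, SAF and SAFT and no per-protocol set. The protocol's abbreviation list does include per-protocol, but no readable section defines or uses it. SAP 5.5 has deviations evaluated before database lock, then tabulated and listed; SAP 7.5 has all medications listed. These may identify the subjects but do not alter the rates.

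**4. Size.** Let x be the counted successes, n the denominator and k the successes reached after prohibited acne therapy. Recoding them gives (x − k)/n, a drop of k/n.

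- n = 50: 1/50 = 2.0 points each.
- OC with n = 40: 1/40 = 2.5 points each.

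The Clopper-Pearson limits are the 0.025 quantile of Beta(x, n − x + 1) and the 0.975 quantile of Beta(x + 1, n − x). Neither x nor k is in the documents. With x between 10 and 25 and k from 0 to 5 as assumptions, and n = 50:

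| Assumed x | k | Rate | 95% CI |
|---|---|---|---|
| 20 | 0 | 40.0% | 26.4–54.8 |
| 20 | 1 | 38.0% | 24.7–52.8 |
| 20 | 3 | 34.0% | 21.2–48.8 |
| 20 | 5 | 30.0% | 17.9–44.6 |
| 10 | 0 | 20.0% | 10.0–33.7 |
| 10 | 5 | 10.0% | 3.3–21.8 |
| 25 | 0 | 50.0% | 35.5–64.5 |
| 25 | 5 | 40.0% | 26.4–54.8 |

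For k from 1 to 5 the difference is 2 to 10 points with n = 50, and 2.5 to 12.5 points under OC with n = 40. The PGA denominator under LOCF and MAF is the ITTT population, whose definition and size are not readable; if it is smaller than 50, each subject weighs more.

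**The case against.** **Using all observed data is legitimate.** Analysing scores regardless of other therapy is a recognised treatment-policy approach, and this is a descriptive trial whose objective is subject-reported outcomes. That stands, and it is why the planned analyses should stay. What is missing is a statement that this is the approach taken, and a figure that shows its effect.

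**The governing text may be redacted.** The prohibited-therapy list, SAP 5.2 to 5.4, and parts of SAP 5.1, 5.5, 6.3, 6.6, 7.5, 8.1.1 and 8.1.2 are blacked out. A reader might infer that the full plan certainly has no rule. The documents do not support that; the point is limited to what can be read.

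**Prohibited does not mean effective against acne.** Because the list is hidden, a reader should not infer that every prohibited therapy raises the success rate. The point applies only to therapies indicated for acne.

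**Two inferences about intent are also unsupported.** Protocol 5.5.4 gives no reason for its condition, so it cannot be cited as saying that acne therapies would distort the outcome. Nor do the documents call the non-responder analysis conservative. It is described as a way of handling missing data, so it is not failing at a task the plan gave it.

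**A contrast with subjects who leave is likely but not established.** One might infer that the same subject, on leaving, would certainly be a Week 24 failure under MAF. SAP 6.6 makes early termination a stand-alone visit for efficacy, but the text after that is redacted and SAP 6.1 allows for tables labelled Week 24/ET.

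**The effect lies within sampling error.** Five subjects move the rate by 10 points, against a half-width of about 14 points at 20/50. That is true, but the interval reflects sampling variation only; it shifts with the recoding and does not allow for it.

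**Conclusion.** The point holds for the readable text. A prohibited acne therapy does not end participation automatically, and a later observed success counts under OC, LOCF and MAF. Without a control arm, the reported IGA and PGA success rates can therefore include clearance reached with other acne treatment, and no planned rate shows how much.

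Each such success is worth 2 points if the denominator is 50. The total is unknown and may be zero; the 2 to 10 point range rests on an assumed one to five subjects. The conclusion also assumes that non-evaluable means lacking data at the visit and that no redacted rule says otherwise. It is a gap in the handling of secondary descriptive results, worth closing because it is cheap to close. It is not evidence that the rates will be materially wrong.

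**What to change.** Keep OC, LOCF and MAF as planned, and add to SAP 6.3, 8.1.1 and 8.1.2:

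- A sentence stating that these three analyses use observed scores regardless of prohibited therapy.
- One pre-specified supplementary non-responder analysis of IGA and PGA success. In it, a subject is a failure at every visit on or after the start of a prohibited therapy indicated for acne vulgaris, whether or not a score was recorded. Keep it separate from MAF, so that one label does not cover both missing data and observed data set to failure.
- A flag for these subjects, derived before database lock from the concomitant-therapy data that Protocol 5.5.3 already has reviewed at each visit, and assigned without sight of the outcomes.
- The number of flagged subjects beside the Week 12 and Week 24 rates.

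If a redacted passage already sets such a rule, cross-refer to it instead.

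The cost is a few sentences, one derived flag and one more table row. The supplementary rate may be slightly lower than the others; if nobody is flagged, it equals MAF provided missing data are handled in the same way. The change concerns data handling only and proposes nothing about who is treated or who continues.

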5.6 Procedures/reasons for subject discontinuation

An Investigator may decide to discontinue a subject from the clinical trial for safety reasons.

Although the importance of completing the entire clinical trial should be explained to the subject by the clinical trial personnel, any subject is free to discontinue his/her participation in this clinical trial at any time and for whatever reason, specified or unspecified, and without any prejudice. No constraints are to be imposed on the subject, and when appropriate, a subject may be treated with other conventional therapy when clinically indicated.

When a subject does not complete the clinical trial, he/she will be fully assessed, if such assessment is possible. The procedures designated for the Week 24/Early Termination visit should be completed for all subjects discontinuing the clinical trial and the appropriate CRF page should be completed.

All discontinuations and the reason for discontinuation are to be documented by the Investigator on the Exit Form, and also on the Adverse Event Form for discontinuation due to an AE.

For discontinuation due to an AE, the Investigator should ensure that the subject receives suitable therapy for his/her AE.

A subject who has been enrolled and assigned a kit number cannot be replaced by another subject if he/she discontinues the clinical trial for any reason.

GALDERMA R&D may also decide to prematurely terminate or suspend a subject's participation in the clinical trial.

Potential reasons for discontinuation, as listed on the Exit Form, are defined in Table 3 below:

Table 3 Exit Form reasons for discontinuation

Pregnancy:	Withdraw the Subject from the clinical trial and follow the procedure described in Section 7.2.2.2.5.
Lack of Efficacy:	Investigator judgment only: based on therapeutic/disease-state expectations. If subject opinion only, mark "subject request" and document it in the comment section of the Exit Form.
Adverse Event:	Complete an Adverse Event Form.
Subject Request ^a :	Includes consent withdrawal, subject relocation, schedule conflicts. Explain the reason for withdrawal in the comment section of the Exit Form. If a subject withdraws consent because of an adverse event, the reason for discontinuation should be Adverse Event
Protocol Violation:	Explain the violation in the comment section of the Exit Form.
Lost to Follow-up:	Confirmed with two documented phone calls and a certified letter (delivery receipt requested) without answer. Explain in the comment section of the Exit Form.
Other ^a :	This category is to be used for a subject who discontinues due to a reason other than as specified in the predefined categories above. Explain the reason for discontinuation in the comment section of the Exit Form.

a) If reason for discontinuation is "subject request" or "other", the subject will be questioned to rule out the possibility of an AE (this should be documented in the comment section of the Exit Form).

6 CLINICAL SUPPLIES

6.1 Clinical supply identification and use

6.1.1 Study drug description

Table 4 Description and usage of the study drug

	Investigational Product
Trade Name or Equivalent	N/A
Name of Drug Substance	Trifarotene
Internal Code	CCI
Pharmaceutical Form	Cream
Strength/ Concentration	50 µg/g
CCI	
Location of Treated Area	Face and truncal region CCI
CCI	

N/A=not applicable

6.1.2 Subject identification number

Upon signature of the ICF (and Assent for minor subjects) each subject will be assigned a Subject Identification Number (SIN) by the designated study personnel.

CCI

6.1.3 Kit number

The kit number, a unique number corresponding to the number on the label of the study drug, will be assigned to each eligible subject at Baseline. CCI

CCI

6.1.4 Instructions for use and application

Each subject will receive both oral and written instructions for the proper dosing and study treatment application techniques. CCI

CCI

As well, the dosing calendar completion will be explained to each subject at each dispensation visit.

Applications will be done by the subjects themselves at home in the evening. CCI

CCI

Application on the face:

CCI

CCI

The study drug will be applied to the facial region which includes the forehead, nose, chin and each cheek once daily in the evening after washing and drying.

The objective is to cover the face with a thin layer of the study drug, CCI One pump actuation should be enough to cover the forehead, right cheek, left cheek, nose, and chin. Avoid application in/close to eyes, or angles of the mouth, lips and mucous membrane.

CCI

Application on the trunk:

CCI

The study drug will be applied to the upper truncal regions CCI once daily in the evening after washing and drying.

The objective is to cover the reachable upper truncal region with a thin layer of the study drug, CCI Two actuations of the pump should be enough to cover right and left upper back area CCI and upper anterior right and left chest. Avoid application on the axillary region and anterior and posterior neck.

The study drug should not be applied to cuts, abrasions, eczematous, or sunburned skin.

The daily diary is to be completed by the subject (if needed, with the help of the legal guardian) and returned to the site at each study visit.

